3.3.1. Reactive case detection (RACD)

Household RACD

Within 7 days of the index case notification, the VMW will conduct the investigation visit at the residence of the index, and the index case will be interviewed using a standard case investigation form. All members of the index case's household will then be invited to participate in the study. A GPS point will be captured for the index house, and the nearest five households around the index case's household will be identified by the VMW. In the neighboring five households, a GPS point will be captured and all household members, including temporary visitors, will be invited to participate in the study. Household members and parents/guardians of children will be verbally informed of the general purpose of the intervention and the study, and the possible risks and potential benefits associated with participation. Individual written consent will be obtained at each household and for each blood sample collected for testing. For children <6 to 12 years old, consent will be obtained from the parent or guardian. For children 12 to <18 years of age, the child's oral assent will also be required in addition to parents/guardians' consent. All informed consent procedures will be conducted in the appropriate local language. All consenting participants will be interviewed using the participants' questionnaire to assess history of malaria in previous year, travel information, and utilization of malaria prevention measures.

A finger stick blood sample will be collected for each consenting individual for testing with the HS-RDT for *P. falciparum*, a standard combination RDT, and four blood spots on filter paper. Individuals will be told of their test result and a positive test result on either RDT will prompt treatment as per the national treatment guidelines. See tables 2 and 3 below for treatment guidelines.

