3.3.2. Adherence and safety monitoring

To ensure participants' adherence to their medication and monitor safety, participants will be informed on how to take their medications, about the side effects of the treatment and the importance of compliance to the treatment. In addition to DOT on day 0, The VMW will conduct a day

3, day 7, and day 14 adherence and safety monitoring visit for all individuals treated with primaquine for *P. vivax*, and the VMW will ask a series of questions to determine adherence with each dose, number of remaining tablets, potential adverse events, and reasons for non-adherence or treatment refusal. Participants with phone number will be sent a daily text message to remind them to adhere to their treatment and remind them about any symptoms suggesting serious adverse events. All participants and their family members will be provided a chart to record and track their adherence as well as symptoms that may indicate an adverse event.

The safety risks associated with participation in this trial are expected to be minimal. The study drugs, AL and PQ, are well tolerated first-line treatments and safe for G6PD non-deficient individuals. Prior to drug administration, participants will be asked about known contraindications, and if such contraindications are reported, participants will be restricted from taking the medication.

Drug	Contraindications
AL	Pregnancy, infants < 5kg, prior allergic reaction, any severe disease
PQ	Pregnancy, age < 12months, infants < 10kg, women in first 12 months of breastfeeding, prior allergic reaction, any severe disease, G6PD deficient

The common adverse events reported for each drug are as below:

- AL: headache, dizziness, loss of appetite, generalized weakness, fever, chills, arthralgia, myalgia, nausea, vomiting, and abdominal pain
- PQ: nausea, headache, fatigue, dizziness, hives, chest pain, painless darkening of urine, jaundice of skin and vomiting.

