The Primaquine Roll Out Pharmacovigilance Tool Data Collection Forms (PROMPT) will be used to track the status of individuals treated with PQ. Identification of serious adverse events (SAEs) will occur both passively and actively. As part of the consent process, participants will be instructed to call or visit VMW to report any adverse events that occur between VMW visits. During adherence and follow up visits, the VMW will also ask participants for specific adverse events related to hemolysis. SAEs as well as serious unexpected serious adverse reactions (SUSAR) will be reported to the study management and PI who will report to the data safety monitoring board (DSMB). At each study site, a local physician will be recruited (Local Safety Monitor, LSM) to determine causality and grade of the SAE. All SAEs will be reported to the Pharmacovigilance center of the Ministry of Health (Lao PDR) and the respective IRBs. All potential AEs or SAEs will be referred by VMW to the nearest health center or district hospital for management and documented as per 4.2 below, and the study will reimburse all patient travel and hospitalization resulting from study drug administration.

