Activity 3: Assessment of the operational feasibility and safety of conducting G6PD testing, referral, and treatment adherence among positive P. vivax RDT cases	1. Assess the operational feasibility of G6PD referral at community level	Proportion of VMWs who rate conducting G6PD referral as very easy, somewhat easy, somewhat difficult, and very difficult, and changes in proportions over time	Entrance, mid-intervention, and exit competency checklists with VMWs; focus group discussion and interviews with VMWs at end-line	
		Proportion of P. vivax cases with valid recorded G6PD result	VMW and health facility records	
	2. Determine risk factors for non-attendance at hospitals or health centers after referral for G6PD testing	Proportion of referred cases presenting at hospitals or health centers for G6PD testing.	Cross-sectional survey and qualitative studies at endline with villagers, forest workers, VMWs	
	3. Assess treatment adherence among positive P. vivax RDT cases	Proportion of patients with physical evidence of full adherence with the prescribed drug regimen	VMW follow-up visits on day 3, 7, and 14	
		Proportion of P. vivax cases who relapsed in the six months following treatment	VMW and health facility records	
	4. Assess the safety of community-level G6PD testing, referral, and P. vivax treatment follow-up	Adverse event rate per treated individual	RACD intervention data and VMW follow-up visits; health facility adverse event reporting forms	
	Activity 4: Assessment of the risk of malaria vector biting in forest and village settings	1. Describe local vector species composition and bionomics in forest and village settings	Vector occurrence and density by species; vector biting behaviors; human behavioral observations in relation to human biting rate (HBR)	Human Landing Catches (HLCs) vector sampling at baseline

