3.4.3.2. Primary outcomes measures

1. Population coverage of enhanced RACD interventions: this indicator will be measured in two ways. Operational program coverage will be defined as the proportion of individuals ≥ 18 months old and households visited and offered the RACD interventions within the target areas per time period. Effective program coverage is defined as the proportion of individuals (≥ 18 months old) that agreed to participate in the RACD intervention among all individuals ≥ 18 months old eligible to participate in the intervention in the target population per time period.
2. Feasibility of conducting enhanced RACD intervention at the community level: feasibility will be determined based upon a combination of population coverage data, responses of provincial, district, and health staff, VMWs, and community members to KIIs and FGDs at baseline and endline, VMW competency checklists at baseline, midline, and endline, and cost data.
3. Acceptability of community-based RACD approaches: acceptability will be determined based upon refusal rates during interventions and responses of community members and VMWs to endline questionnaire, interviews, and focus groups.
4. Safety of community-based RACD and treatment follow-up: safety measures will include the adverse event rate amongst treated individuals and hemoglobin measurement pre and post treatment for individuals receiving PQ.
5. Operational feasibility of G6PD referral: operational feasibility of G6PD referral will be determined by the results of the process-mapping and co-design workshops at baseline, responses of health staff and VMWs to interviews and focus groups at baseline and endline and competency checklists at baseline, midline, and endline, the proportion of referred *P. vivax* cases presenting at a health facility for G6PD testing, and the proportion of *P. vivax* cases with a valid recorded G6PD result.
6. Assessment of *P. vivax* treatment adherence: treatment adherence will be determined by the proportion of *P. vivax* cases with physical evidence of adherence through pill count, the *P. vivax* relapse rate across study arms, and the proportion of *P. vivax* cases with successful parasite clearance on day 14.

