The adverse event rate for RDT positive participants will be assessed using intervention data and health facility adverse event reporting forms. Study staff and VMWs will be trained on detection of adverse events for positive cases receiving treatment.

Outcome 5: Operational feasibility of G6PD referral, testing and non-adherence

The operational feasibility of G6PD referral, testing and non-adherence at the community and facility levels will be evaluated. For testing, interview data at baseline and endline will be collected from district health staff and community members, as well as focus group discussions with both groups at end-line. Risk factors for non-adherence to G6PD testing after referral will be determined through comparison of factors captured at enrollment for individuals who were tested at a facility versus those who were not.

Outcome 6: Assessment of *P. vivax* treatment adherence

The treatment adherence of *P. vivax* positive study participants will be assessed through physical evidence of adherence during VMW follow-up visits on day 3, 7 and 14 and comparison of relapse rates across study arms.

3.4.4. Assessment of the risk of malaria vector biting in forest and village settings

A baseline entomological investigation will be conducted along with the baseline qualitative activities in Aug/Sep 2019. The investigation will involve collection of vector occurrence and density data (by species), human landing catches (HLC) to assess vector biting behaviors (indoor vs outdoor and forest sites), and household structure type, and human behavioral observations. All collections will take place over a one-week period. HLC collections will occur in 4-5 sleeping structures each in the forest and village, with 2 HLC collectors by structure. At the end of each HLC collection hour, collectors will also record human behavior (sleeping (or awake) under net/sleeping without net/awake), both indoors and outdoors. Field collectors will be community volunteers that will have been properly informed about the sampling methods and their implications, and who have consented to participating by signing consent forms. Prior to the start of collections, volunteers will also need to be tested for malaria. Depending on national policy, they may also be required to take malaria prophylaxis. HLC data collection forms are found in the Appendix.

4 Ethical issues related to human subjects research

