5.1. Potential risks from participation

Detailed discussion of potential AEs related to drug regimens is discussed above in section 4.2. Finger pricks for RDTs and DBS are associated with small risks of bleeding, hematoma, and infection. To minimize these risks, the skin will be cleaned with alcohol prior to puncture, and sterile unused lancets will always be used, and pressure will be placed on the puncture site after removal of the lancet using sterile gauze. Although the quantity of blood drawn would not lead to any ill effects on the participants' health, some adults and rarely children feel faint from the blood during the finger prick. The risks will be minimized by having trained health staff perform all procedures, and all untoward effects will be evaluated by health center staff.

For those subjects with *P. vivax* diagnosis that are tested for G6PD deficiency, there is a risk of misclassification and wrongly ascribed to being G6PD non-deficient and then being treated with 14 days of PQ. In this study, the team will ensure a high-quality of training for all those using the G6PD RDTs, in addition subjects will be given information on what to do if they experience adverse events, and on days 3 and 14 all subjects given PQ will be actively followed up. If hemolysis is suspected PQ treatment will be stopped and the subject monitored to at least day 14. Should the hemolysis event require further clinical management, the study team will ensure access to appropriate health services.

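### The adverse event rate is defined per treated individual but analysed for RDT-positive participants, and the named pre/post haemoglobin measure has no described collection and no analysis

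*Protocol*

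**What the plan says.** The outcome is defined twice in the same way. The evaluation table in Protocol 3.4.1 (Activity 3) gives "Adverse event rate per treated individual". Section 3.4.3.2, item 4, says "safety measures will include the adverse event rate amongst treated individuals and hemoglobin measurement pre and post treatment for individuals receiving PQ".

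The analysis paragraph for this outcome (3.4.3.5, Outcome 4) uses another population: "The adverse event rate for RDT positive participants will be assessed using intervention data and health facility adverse event reporting forms". Its next sentence returns to treated people: "Study staff and VMWs will be trained on detection of adverse events for positive cases receiving treatment". Haemoglobin is not mentioned there.

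On data collection, household RACD testing in 3.3.1 lists "testing with the HS-RDT for *P. falciparum*, a standard combination RDT, and four blood spots on filter paper". The follow-up visits in 3.3.2 are for people given PQ for vivax, and at them "the VMW will ask a series of questions to determine adherence with each dose, number of remaining tablets, potential adverse events". The same section adds that "the VMW will also ask participants for specific adverse events related to hemolysis". A Hemocue kit is named only for the endline cross-sectional survey (3.4.2.5.2).

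On timing, 3.3.2, 3.4.3.5 (Outcome 6) and 4.2 place the visits on days 3, 7 and 14. Section 5.1 says "on days 3 and 14 all subjects given PQ will be actively followed up".

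**The concern.** A rate per treated person and a rate per test-positive person answer different questions. Only the first describes the safety of the drugs as given. An analyst who follows 3.4.3.5 literally puts people who took nothing into the denominator. They cannot have a drug-related event, so the rate falls for a reason unrelated to safety.

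The haemoglobin gap is a separate defect and does not affect the denominator. Section 4.2 names acute haemolytic anaemia in G6PD-deficient people as the main concern with PQ, and pre/post haemoglobin is the one quantitative measure of it among the safety outcomes. If nobody is instructed to take it, the outcome cannot be reported.

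At stake is the secondary objective on the safety of G6PD testing, PQ administration and follow-up at community level.

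**Working it through.** **No figure to reproduce.** The protocol states no adverse event rate, no treated share of RDT-positives and no sample size for this outcome. The check is therefore a comparison of the text, then an illustration.

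**Who is RDT-positive but may be untreated**
- Vivax cases: 3.3.1 sends them by letter to a facility, where both artemether-lumefantrine (AL) and PQ are given. Whether they present there is itself an outcome in 3.4.1, so non-attendance is expected.
- People with severe disease or drug contraindications: 3.2 excludes them from the treatment component only, so they remain participants.
- Women excluded from AL because of pregnancy or a refused pregnancy test: 3.3.1 refers them to a facility for treatment. They are untreated on site but not necessarily untreated afterwards.

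**Formula.** If events arise only in treated people,

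rate per RDT-positive = rate per treated person × share of RDT-positives treated.

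The relative understatement equals the untreated share, whatever the event rate.

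**Illustration: vivax non-attendance only**
- Vivax share, Table 1 totals: 2.79 / 6.77 = 0.412. Assumption: RACD positives have the same species mix.
- Attendance after referral, *a*: not in the protocol. Assumption: 30% to 90%.
- Untreated share = 0.412 × (1 − *a*). Dilution = 1 / (1 − untreated share).

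| Attendance | Untreated share | Dilution | A true 5% per treated would read |
|---|---|---|---|
| 30% | 0.412 × 0.7 = 0.288 | 1 / 0.712 = 1.40 | 3.6% |
| 50% | 0.412 × 0.5 = 0.206 | 1 / 0.794 = 1.26 | 4.0% |
| 90% | 0.412 × 0.1 = 0.041 | 1 / 0.959 = 1.04 | 4.8% |

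The 5% is assumed and serves only to show scale. If every positive is treated, the dilution is nil.

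**Haemoglobin, section against section**
- Named as a safety measure: 3.4.3.2, item 4.
- Possible pre-treatment point: RACD testing in 3.3.1 lists RDTs and blood spots only.
- Possible post-treatment point: the visits in 3.3.2 consist of questions and a tablet count.
- Analysis: none in 3.4.3.5.
- The endline Hemocue is a population survey measurement. It is not paired with treatment.

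**Follow-up days.** Section 5.1 omits day 7, which 3.3.2, 3.4.3.5 and 4.2 include.

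**The case against.** The best defence is that three statements (3.4.1, 3.4.3.2 and the second sentence of Outcome 4) point to treated people, against one loose phrase. That is fair. Dilution is what happens if the phrase is followed, and the denominator is contradictory, not settled. But the phrase stands in the sentence that sets the analysis, so it needs correcting.

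The inputs of the illustration are also open to challenge, and this stands. Table 1 describes annual case incidence, while RACD adds a high-sensitivity test for falciparum only. After six months a subset of village malaria workers (VMWs) test and treat in the community, so referral attendance would not apply to every vivax case. The table shows a range, not an estimate.

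Four stronger readings are tempting, and the documents do not support them.

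- **A several-fold dilution.** Assume 50% attendance, 4.2% G6PD deficiency (section 2), and a 5% event rate on 14-day PQ with none elsewhere. The share on 14-day PQ is 0.412 × 0.958 × 0.5 = 0.197, so the pooled rate is 5% × 0.197 = 0.99%. With treated people as denominator it is still only 0.99% / 0.794 = 1.24%. Most of the gap comes from pooling regimens, on which the protocol does not contradict itself. Assuming no events elsewhere also conflicts with 3.3.2, which lists common adverse events for AL.
- **A contradiction over who is followed.** Section 5.1 refers to everyone given PQ, but its paragraph opens with vivax subjects tested for G6PD deficiency and concerns the 14-day course. In context the population matches 3.3.2; only day 7 differs.
- **Haemolysis judged from symptoms alone.** Potential events are referred to a facility (3.3.2), clinical records and laboratory reports accompany forms sent to the safety board (4.2), and serious events with suspected haemolysis lead to G6PD genotyping (3.4.2.7).
- **Haemoglobin not taken at all.** The adherence form and the PROMPT form (Appendices 8.24 and 8.25) are listed but not shown. What can be said is that no procedure in the protocol describes it.

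**Conclusion.** Two defects hold.

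First, the denominator in 3.4.3.5 contradicts the definition in 3.4.1 and 3.4.3.2. Taken literally, it understates the adverse event rate by the untreated fraction. The protocol does not give that fraction. Under the assumptions above it is 4% to 29%, and contraindications or severe disease could add to it. This is a modest bias of known direction in a descriptive safety summary. It does not touch the stopping rule in 4.5, which rests on a separate comparison between arms.

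Second, pre/post haemoglobin in PQ recipients is a named safety measure with no described collection point at RACD or PQ visits and no analysis. This rests on the protocol text, since the data collection forms are not shown.

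The omission of day 7 in 5.1 is a smaller inconsistency that also needs reconciling.

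**What to change.** 1. In 3.4.3.5, Outcome 4, replace the RDT-positive population with participants who took at least one dose of study drug.
2. Report the rate by regimen received: AL plus single-dose PQ, AL plus 14-day PQ, and AL alone. This goes beyond removing the contradiction. It is worth doing because risk differs between regimens, and the scheduled visits in 3.3.2 are described only for people given PQ for vivax.
3. Reconcile 3.4.3.2 with the procedures in 3.3.1 and 3.3.2 and with 3.4.3.5 on haemoglobin. Otherwise, limit the safety conclusion to reported and facility-documented events.
4. Reconcile the follow-up days in 5.1 with 3.3.2, 3.4.3.5 and 4.2.

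**Cost.** The denominator change is wording. Reporting by regimen gives smaller groups and wider intervals. PROMPT tracks PQ recipients (3.3.2), but nothing shown confirms that dosing and events are recorded for people given AL alone, so the sponsor should check this before adopting the new denominator. Items 3 and 4 mean edits to the procedural sections as well as the analysis section.

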Research objectives	
Primary Objective: To evaluate the effectiveness of reactive case detection (RACD) using HS-RDTs, targeting both village and forest working populations, compared to control for reducing the health center catchment-level incidence and prevalence of P. falciparum and P. vivax within two provinces in Lao PDR.
 
Secondary Objectives:
 
 1. To determine the operational feasibility, cost-effectiveness, and acceptability of targeting high-risk populations with community-based reactive case detection strategies aimed at reducing P. falciparum and P. vivax transmission among village and forest working populations. 2. To determine the operational feasibility and safety of conducting G6PD testing and PQ administration and follow-up at the community level. 3. To determine factors associated with G6PD testing after referral to district or provincial-level facilities for persons with P. vivax positive RDT results, and subsequent adherence to Primaquine treatment. 4. To assess malaria vector species composition and bionomics in both village and forest settings
Study site and target populations	Total population of approximately 120,000 in 32 health center catchment areas of two Provinces in Lao PDR (Champasak and Saravan Province)
Study design	A cluster randomized controlled trial design will be used to evaluate the enhanced RACD intervention against standard of care
Primary outcome measures for assessing impact	
 1. Cumulative incidence over the study period at the health facility level 2. Prevalence of infection (P. falciparum and/or P. vivax) using qPCR 3. HS-RDT and RDT test positivity rate for RACD
Data collection and sampling period	18 months from start date (June 2019 – November 2020)

Sample size	32 health center catchment areas in Lao PDR

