2.5. Study overview

To test this hypothesis, this study will employ a cluster randomized controlled trial design with two comparison arms:

1. **Control:** standard of care - passive case management provided through community-based VMWs and existing health facilities; includes village-based RACD with conventional RDTs conducted by district surveillance teams.
2. **Enhanced community-based RACD:** RACD conducted by community-based VMWs using both HS-RDTs and conventional RDTs within villages and among forest workers.

The primary outcome measures to assess effectiveness include *P. falciparum* and *P. vivax* confirmed case incidence over the study period; PCR-based *P. falciparum* and *P. vivax* prevalence at endline; and HS-RDT test positivity rate in village and forest worker RACD. Secondary outcomes measures will examine the operational feasibility, safety, and acceptability of VMW-led reactive approaches and G6PD testing, referral to district or provincial-level facilities, safety and treatment adherence for *P. vivax* cases. The trial will be implemented between June 2019 and December 2020 in Lao PDR. The primary evaluation will be conducted following an end-line cross-sectional survey in November/December 2020.

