All individuals who test positive by either HS-RDT or Standard RDT will be told of their results and treated on site per national guidelines:

- Individuals with *P. falciparum* infection will be treated with an age-appropriate course of artemether-lumefantrine (AL) and a single low dose of primaquine (SLD-PQ). Weight-based dosing is described in Tables 2 and 3 below.
- At all study sites in Lao PDR, patients with a *P. vivax* infection identified by RDT (both febrile and asymptomatic) will be given a unique coded and signed informational letter directing them to the nearest district hospital (or other testing facility) for G6PD deficiency testing and possible radical cure administration depending on results. Study contact information will also be included if the participants present at other health facilities. At the health facility, G6PD normal individuals will be treated with AL and a 14-day course of PQ, whereas G6PD deficient individuals will receive AL alone as per the national guidelines and referred to a hospital for further primaquine management decisions. The study staff will meet with district hospital and health facility staff monthly from all study areas and nearby district hospitals and health facilities to collect these forms, with small incentives for health staff to report receiving a study card (phone top up card, etc.) to maximize data completeness. After six months of implementation, a subset of VMWs will begin conducting qualitative G6PD testing and treatment administration at the community-level with the assistance of a health facility staff member.

Table 2. AL weight-based dosing

Body weight (kg)	Tablet strength (mg)		Tablets/dose	Mg of drug per dose		Tablets/day
	Artemether	Lumefantrine		Artemether	Lumefantrine	
5 to 14	20	120	1	20	120	1 tablet given twice* per day for 3 consecutive days

15 to 24	20	120	2	40	240	2 tablets given twice* per day for 3 consecutive days
25 to 34	20	120	3	60	360	3 tablets given twice* per day for 3 consecutive days
35 or greater	20	120	4	80	480	4 tablets given twice* per day for 3 consecutive days
*Approx. 8 hours between doses 1 and 2. Approx. 12 hours between all other consecutive doses.						

Table 3. Weight-based dosing of SLD- Primaquine (.25 mg/kg) for *P. falciparum*

Body weight (kg)	SLD-PQ dose (7.5 mg tablet) (as base)	Tablets
10 to < 25	3.75	1/2
25 to < 50	7.5	1
50 to 100	15	2
*Given as SLD in addition to AL for P falciparum positive		

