3.4.2.5.3. Intervention implementation data

Data collection during RACD activities is described below.

Questionnaires and human specimen collection: reactive case detection (RACD)

For all household members and co-worker referrals from forest workers in RACD intervention areas, after obtaining informed consent, a short demographic and malaria risk factor survey will be conducted to obtain information on individuals' occupations, recent forest work or travel, ITN usage, and recent care-seeking behavior for fever. Household members and referrals will be linked to the index case through unique codes in order to facilitate follow-up and allow for statistical adjustments, such as clustering by index case.

In the intervention areas, all patients with a *P. vivax* positive RDT will be given a coded and signed informational letter directing them to the nearest health center of hospital for G6PD testing and follow-up treatment. All *P. vivax* patients will be recorded into a registry and given an identification card for presentation and treatment and follow-up visits.

Sites where interviews occur will be geo-located if all parties agree. VMWs may also obtain contact information from consenting persons to allow for follow-up on positive cases and potential creation of support networks for other HRPs.

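### The between-arm P. vivax relapse comparison draws on different kinds of case and different chances of recording a recurrence in each arm, so a crude difference cannot be read as a difference in adherence or radical cure

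*Protocol*

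**What the plan says.** Section 3.4.3.2 (item 6) lists three components of P. vivax treatment adherence: pill count, the "relapse rate across study arms" and day-14 parasite clearance. Section 3.4.3.5 (Outcome 6) repeats the contrast as a "comparison of relapse rates across study arms". The Activity 3 rows of the overview table in section 3.4.1 fix the measure as the proportion of "cases who relapsed in the six months following treatment", with "VMW and health facility records" as the source.

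On who is a case, section 3.3.1 describes RDT-positive P. vivax patients as "both febrile and asymptomatic", and in the enhanced arm RACD reaches neighbouring households and forest co-workers. Section 3.4.2.5.3, in a paragraph that opens with the intervention areas, says that P. vivax "patients will be recorded into a registry and given an identification card for presentation and treatment and follow-up visits". The eligibility criteria in section 3.2 are written for enhanced RACD only. Control care is passive detection plus village RACD by district teams (section 2.5), which Table 5 limits to some areas.

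On timing, the protocol summary gives data collection as "18 months from start date (June 2019 – November 2020"). Section 2.5 says "The trial will be implemented between June 2019 and December 2020 in Lao PDR".

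**The concern.** A relapse proportion can be compared between arms only if the people in the denominator are of the same kind and a recurrence has the same chance of being recorded. Neither condition is secured here. The intervention itself changes which P. vivax infections become cases, and it adds later opportunities to find a recurrence.

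This comparison is the protocol's between-arm evidence on radical-cure adherence. If true relapse were equal, more complete recording in the enhanced arm would make radical cure look worse there. A different mix of symptomatic and asymptomatic infections could move the result either way. The contrast, measure, window and source are all stated, so this is a comparison fixed in a form that cannot be interpreted, not merely a detail left open.

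A second, smaller question is how much of the six-month window can be seen for cases treated late in the trial.

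**Working it through.** **1. The two arms side by side**

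| | Enhanced arm | Control arm |
|---|---|---|
| How cases arise | Index cases, plus VMW-led RACD in villages and among forest workers (2.5, 3.3.1) | Passive care, plus district-team village RACD (2.5) in some areas (Table 5) |
| Forest co-workers tested | Yes | Not described |
| P. vivax registry | Described (3.4.2.5.3) | Not described |
| Defined cohort | Criteria in 3.2 | None stated |
| Active re-testing | Barred only for 30 days after an RACD event (3.2) | Depends on district teams |

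Taking 30 days as one month, a person first found in RACD can be actively re-tested during 5 of the 6 months in which relapse is counted. The high-sensitivity RDT detects P. falciparum only, unless a P. vivax version becomes available (3.4.2.7). The P. vivax difference therefore comes from the wider reach of RACD using the standard RDT.

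**2. What unequal recording does**

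Observed proportion = true proportion × share of recurrences recorded. With equal true relapse, the observed ratio is simply the ratio of the recording shares. The protocol gives no such shares, so these values are assumptions that show scale only. With a true six-month relapse of 20% in both arms:

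- 50% recorded in each arm: 10% v 10%, ratio 1.0.
- 65% (enhanced) v 50% (control): 13% v 10%, ratio 1.3.
- 80% v 50%: 16% v 10%, ratio 1.6.

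**3. The observation window**

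Reproducing the stated period: June to December 2019 is 7 months and January to November 2020 is 11, total 18. A full six months by the end of November 2020 needs treatment by about the end of May 2020.

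Share of accrual time with an incomplete window = (window − months of record collection after accrual ends) / accrual months:

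- Accrual and records to November 2020: 6/18 = 33.3%.
- Accrual and records to December 2020: 6/19 = 31.6%.
- Accrual to November, records to December 2020: (6 − 1)/18 = 27.8%.
- Window counted from the end of the 14-day course, November end: (6 + 14/30.4)/18 = 35.9%.
- Accrual to November 2020, records read to March 2021: (6 − 4)/18 = 11.1%.

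**4. Effect on a plain proportion that keeps late cases**

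Assume uniform accrual and relapse times spread evenly over six months. Late cases are then seen for half the window on average, and the share of relapses seen is 12/18 + (6/18) × 0.5 = 83%. With records read to March 2021, late cases have on average 5 of 6 months, giving 16/18 + (2/18) × (5/6) = 98%.

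If instead 20% of cases fall in the last six months, the share seen by November 2020 is 0.80 + 0.20 × 0.5 = 90%. If 50% do, it is 0.50 + 0.50 × 0.5 = 75%.

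**5. Effect on the contrast**

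With the same case timing in both arms, the factor cancels: 0.83/0.83 = 1. With 20% late cases in one arm and 50% in the other, the spurious ratio is 0.90/0.75 = 1.20. No figure in the protocol shows that timing will differ to this extent.

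**The case against.** The strongest reply is that analysis populations and censoring are normal SAP content, and the SAP is not at hand. That stands for the window: sections 3.4.3.2 and 3.4.3.5 speak of rates, which would allow person-time or censored analysis. It does not fully answer the case-mix problem. The protocol already fixes the contrast and its source, and a SAP can repair it only if the mode of detection is recorded for cases and recurrences in both arms.

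Four stronger readings are tempting, and the documents do not support them.

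- **Late cases are unobservable, or are counted as non-relapsed.** They have a partial window, and no sentence says how they are counted. Routine records could also be read later: the timeline has a column for the first quarter of 2021, although the protocol does not plan later reading for this outcome.
- **The 17% understatement is a bias between arms.** Under uniform accrual it is equal in both arms and cancels.
- **Control has no active detection or linkage.** Standard care includes some village RACD. Household ID cards go to all study catchments (3.4.2.5.2), and case capture covers all reporting units (3.4.2.5.1).
- **The day 3, 7 and 14 visits create the difference in detection.** Section 3.3.2 sets them for everyone treated with primaquine for P. vivax, without a clear restriction by arm, and they end too early to detect relapse over six months.

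It is also fair to say that relapse is one of three components of the last of six feasibility and safety measures, with no stated power.

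**Conclusion.** The point holds. Run as a crude comparison, the relapse contrast differs by arm in both its denominator and its chance of recording a recurrence, so a difference would not be evidence about adherence or radical cure. This rests on the stated design differences: the reach of RACD, the 30-day re-test rule and the registry described for intervention areas. It does not depend on any capture rate. The size is unknown, and the ratios of 1.3 to 1.6 only illustrate assumed recording shares.

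The window is secondary. For records ending in 2020, 28% to 36% of accrual time is incomplete; reading records to March 2021 would cut this to about 11%. A plain proportion would show about 83% of six-month relapses under uniform accrual with records to November 2020. That understates the level in each arm, but it distorts the contrast only if case timing differs by arm.

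Priority is minor to moderate. The impact outcomes in section 3.4.2.3 are not affected.

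**What to change.** In section 3.4.3.5, Outcome 6, replace the open comparison with wording to this effect:

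*The between-arm comparison will include P. vivax cases detected passively in either arm. The event is the first passively recorded P. vivax recurrence within six months of treatment, taken from the same health facility and VMW registers in both arms. Six-month proportions will be Kaplan-Meier estimates censored at the register cut-off date; alternatively, only cases treated at least six months before that date will be included. RACD-detected cases will be reported descriptively.*

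State the register cut-off date, and record the mode of detection (passive or RACD) for each case and each recurrence in both arms.

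The text should also acknowledge what remains. A recurrence found and treated through RACD may never present passively, so some difference in detection persists. A sensitivity analysis that counts recurrences from any source would show how much this matters.

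The cost is a change of wording, one detection-mode field in the registers if it is not already there, and fewer cases in the comparison.
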